In addition to patient anatomy the size of the tumor as well as the anatomic location of the tumor are subject to change during radiation treatment. Fox et al. demonstrated a median GTV reduction of 44.3% at 50Gy in patients with non-small cell lung cancer. Head and neck cancers and cervical cancers are particularly sensitive to radiation effects. Barker et al. demonstrated a 69.5% reduction in GTV volume with a median mass displacement of 3.3mm at the end of radiation treatment in patients with head and neck cancers. Cervical cancers have a median mid treatment regression rate of 69% at 36-45Gy when treated with radiation alone and 79% when treated with concurrent chemoradiation (Nam). The resulting anatomic changes during radiation treatment can have a significant impact on dosimetric distributions, resulting in inadequate dose delivery to the tumor even with 4D CT image guided radiotherapy planning (Britton). Britton et al. evaluated the dosimetric consequences of anatomic changes during conformal photon beam radiotherapy for 10 patients with NSCLC using weekly 4D CT Scans. The authors noted a substantial decrease (-20.5%) in the PTV dose coverage and variable increases in dose to normal tissue structures such as the lung, spinal cord, esophagus and heart. These variations were due to inter and intrafractional variations during treatment.

Ideally, one would account for both inter-and intrafraction variability on a daily basis or after a given number of fractions. (Vanuytsel, Vansteenkiste et al. 2000) This could widen the therapeutic ratio by maximizing dose to the tumor and protecting critical normal structures. Harsolia et al. found that in the treatment of patients with NSCLC, daily respiratory motion and tumor volume correction yielded the maximal decrease in treatment volumes (44% reduction) and the maximal decrease in volume normal lung irradiated (31% reduction) and mean lung dose (31% reduction).

At present, the standard of care is to base the entire course of radiation treatment upon the initial treatment plan, which is derived from the pre-treatment scan. It is easy to envision that treatment re-planning to adjust for anatomical changes may be necessary during the course of radiation treatment. The overall objective of this study is to determine the

**Quantification of Tumor and Organ at Risk (OAR) Volume and Motion Path Changes during Definitive Photon or Proton Beam Radiotherapy**

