## Quantification of Tumor and Organ at Risk (OAR) Volume and Motion Path Changes during Definitive Photon or Proton Beam Radiotherapy

imaging will be employed as indicated, at the discretion of the treating radiation oncologist. Photon beam treatment plans and Proton beam treatment plans will be generated from these images. Based on the location of the primary tumor, patients will undergo either up to weekly 3D or 4D CT and/or serial MR scans during treatment. These images will be compared to the initial CT/MR scans used for treatment planning and analyzed for changes in tumor volume and tumor anatomic location. At the end of treatment, the frequent 3D or 4D CT and/or serial MR images will be compared to the initial treatment planning images to quantify the changes in tumor volume and tumor motion during the course of radiation treatment. Each CT and/or MR Scan will also be used to evaluate the changes in dose distribution to the target volumes and normal tissues that occur with the initial photon treatment plan and initial proton treatment. The changes in tumor volume, tumor motion and dose distribution during the course of radiation treatment will be analyzed to determine the effect of tumor changes on radiation treatment efficacy.

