### **6.6. *On Treatments***

Based on the primary tumor location and the discretion of the treating radiation oncologist, patients will undergo 3D/4D CT Scan (up to weekly) and/or MR Scan (minimum of 3).. The GTV, ITV and critical normal structures will be contoured on each up to weekly/serial scan. The up to weekly/serial GTV volume will be compared to the initial GTV volume to determine changes in tumor volume. Each GTV will be compared to the initial ITV volume to determine what percent of the GTV resides within the initial ITV. This value will be used to evaluate changes in tumor motion. Each ITV will be compared to the initial ITV. The initial photon treatment plan and proton treatment plan will be applied to the new scan. The amount of radiation dose to each GTV, ITV and critical normal structures will be recorded to determine the changes in dose distribution that occur as treatment progresses. **SUBJECTS WILL RECEIVE ALL SCANS IN THE RADIATION ONCOLOGY CLINIC OF THE UNIVERSITY OF PENNSYLVANIA.**

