### **9.3 *Objectives:* To determine changes over time in:**

1. tumor volume variables
2. tumor motion
3. patient anatomy
4. dose distribution to tumor and critical normal organs

**9.4 Endpoints:** To be measured at baseline and then weekly during 7-8 weeks of radiotherapy

1. GTV (gross tumor volume), the volume of the primary tumor visualized on the CT scan
2. ITV (interior tumor volume), the GTV expanded to include interior motion (i.e., breathing or swallowing) such that the tumor resides within the ITV during normal motion
3. CTV (clinical tumor volume), the ITV expanded to include microscopic disease (margins)
4. PTV (planning tumor volume), the CTV expanded by several mm, as determined by radiation dosimetry planning, PTV is considered the ultimate target volume

NOTE the relationship: GTV < ITV < CTV < PTV

5. Dose coverage: at each scan time point, determine the percent of the GTV which resides within the baseline ITV or CTV
5. patient weight and percent weight loss from baseline
6. Radiation dose to critical normal organs based on dose-volume histograms (i.e., 20 Gy to 50% of normal lung tissue)

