**9.5 Plans for Data Analysis: To be conducted within each stratum**

1. Tumor Volume: To determine the distributions of volume variables and percent change from baseline. At each scan time point, compute mean, median, range and standard deviation of these variables and plot mean values over time. To compare volume variables at baseline to the values at selected scan time points by paired Wilcoxon signed ranks test.
2. Tumor Motion: At each scan time point, compute mean, median, range and standard deviation of the dose coverage and plot mean values over time. To compare ITV or CTV variables at baseline to the GTV at selected scan time points by paired Wilcoxon signed ranks test.
3. Patient Anatomy: To determine the distribution of patient percent weight loss. At each scan time point, compute mean, median, range and standard deviation of percent weight loss and plot mean values over time.
4. Dose distribution: To determine the distributions of radiation dose to GTV, ITV and critical normal organs. To correlate radiation dose to normal organs with percent weight loss.
5. Conduct exploratory longitudinal analyses to examine changes over time in the 30 patients. Random effects linear regression models will be employed to estimate changes in variables over time clustered by patient. Natural log transformation will be applied prior to modeling.
6. To assess if changes in volume variables are clinically relevant and if so, identify the earliest time point at which re-calibration is warranted. Although it may not be possible to identify a single 're-calibration solution' for all patients in a particular stratum, we will attempt to identify the earliest scan time point at which the majority of patients have clinically important changes in tumor volume or location resulting in over-shoot of the target volume and/or increased dose exposure to normal organs.

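### On-treatment dose is recorded and analysed for the GTV and ITV but not for the CTV or PTV, so loss of coverage at the margin volumes may go undetected

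*Combined protocol and SAP*

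**What the plan says.** Section 6.6 sets what is drawn on each on-treatment scan: "The GTV, ITV and critical normal structures will be contoured on each up to weekly/serial scan". The initial photon and proton plans are then applied to that scan, and "The amount of radiation dose to each GTV, ITV and critical normal structures will be recorded". The analysis plan keeps to the same list. Section 9.5 item 4 reads: "To determine the distributions of radiation dose to GTV, ITV and critical normal organs".

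Other parts of the document are broader:

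- Section 4.0 says each scan will be used to "evaluate the changes in dose distribution to the target volumes and normal tissues" under the initial plans. The Methods overview and the Abstract say much the same.
- Section 9.4 lists GTV, ITV, CTV and PTV as nested volume endpoints, "To be measured at baseline and then weekly during 7-8 weeks of radiotherapy", and adds that "PTV is considered the ultimate target volume".
- Section 9.4 item 5 is labelled as dose coverage but is a geometric overlap: "Dose coverage: at each scan time point, determine the percent of the GTV which resides within the baseline ITV or CTV". Section 9.5 item 2 uses it for tumor motion.
- Section 2.0 motivates the study with a photon series that found "a substantial decrease (-20.5%) in the PTV dose coverage", and with a proton series whose conclusion concerned CTV coverage.

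**The concern.** The Aim 1 hypothesis is that anatomic change may limit dose to the target volumes. The Aim 2 hypothesis is that the effect is greater with protons. The only target doses recorded on treatment belong to the two innermost of four nested structures, and both are redrawn as the tumor shrinks. When a target shifts or changes shape, coverage is lost first at the outer structures, while a smaller GTV and ITV sit deeper inside the region the initial plan irradiates.

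Two things are at stake. A report based on GTV and ITV dose alone could describe target dose as preserved when margin coverage has fallen. And the study could not be compared with the PTV and CTV results it cites, because it would hold no dose data on those structures.

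**Working it through.** **Step 1. Compare the lists.**

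| Place | CTV and PTV included? |
|---|---|
| 6.6, contoured on each scan | No |
| 6.6, dose recorded | No |
| 9.5 item 4, dose analysed | No |
| 9.4 items 3-4, volume endpoints | Yes, as volumes |
| 9.4 item 5, geometric overlap | Baseline CTV as an optional reference; no dose |
| Methods overview, 1.0, 4.0 | Target volumes in general |

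No section provides for recording or analysing on-treatment dose to the CTV or PTV. This part of the point needs no model.

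**Step 2. Can the omission matter?** The plan gives no expected coverage, so there is no figure to reproduce. What follows is an illustration.

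Inputs from Section 2.0: GTV reductions of 44.3% (NSCLC) and 69.5% (head and neck), and a median displacement of 3.3 mm (head and neck).

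Assumed inputs: spherical structures with baseline radii GTV/ITV/CTV/PTV of 3.0/3.5/4.1/4.6 cm (large) or 2.0/2.5/3.0/3.5 cm (small); the baseline PTV stands in for the prescription-dose region; a rigid shift d; no density or range effects.

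Formulas:

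- Shrunken GTV radius = baseline radius × (1 − reduction)^(1/3). The factor is 0.557^(1/3) = 0.823 or 0.305^(1/3) = 0.673. The weekly ITV is the weekly GTV plus 0.5 cm.
- A structure of radius r lies wholly inside the dose region of radius R when r + d ≤ R.
- Otherwise overlap volume = π(R + r − d)²(d² + 2dr − 3r² + 2dR + 6rR − 3R²)/(12d), divided by (4/3)πr³.

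Large tumor, 44.3% shrinkage (the less favourable case for GTV and ITV), d = 1.0 cm, R = 4.6 cm:

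- GTV: 3.0 × 0.823 = 2.47, and 2.47 + 1.0 = 3.47 ≤ 4.6, so 100%.
- ITV: 2.97 + 1.0 = 3.97 ≤ 4.6, so 100%.
- CTV at baseline size, r = 4.1: π × 7.7² × 17.65/12 = 274.0 cm³, over 288.7 cm³ = 94.9%.
- PTV at baseline size, r = R = 4.6: 1 − 3/(4 × 4.6) + 1/(16 × 4.6³) = 83.8%.

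All results with CTV and PTV at baseline size (GTV and ITV hold for both shrinkage figures unless noted):

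| Tumor | Shift | GTV | ITV | CTV | PTV |
|---|---|---|---|---|---|
| Large | 0.33 cm | 100% | 100% | 100% | 94.6% |
| Large | 0.5 cm | 100% | 100% | 100% | 91.9% |
| Large | 1.0 cm | 100% | 100% | 94.9% | 83.8% |
| Large | 1.5 cm | 100% | 100% | 86.5% | 75.8% |
| Small | 0.33 cm | 100% | 100% | 100% | 92.9% |
| Small | 0.5 cm | 100% | 100% | 100% | 89.3% |
| Small | 1.0 cm | 100% | 100% | 92.8% | 78.7% |
| Small | 1.5 cm | 100% | 99.2% (44.3% shrinkage) or 100% | 81.0% | 68.3% |

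The CTV is untouched up to 0.5 cm because the assumed CTV-to-PTV margin is 0.5 cm.

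**Step 3. Change the reference volume.** Rebuild the CTV and PTV from the shrunken GTV with the same margins and keep d = 1.0 cm. With 69.5% shrinkage, the CTV is 100% covered in both tumors and the PTV 100% (large) or 96.1% (small). With 44.3% shrinkage, the CTV is 100% or 99.2% and the PTV 95.5% or 89.1%. Much of the loss in Step 2 thus depends on which reference volume is used, and the plan does not specify one for dose.

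**The case against.** The strongest reply is that the gap is one of wording in a descriptive pilot, and that the illustration is chosen to look bad. Several parts of that stand.

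- The itemised CTV losses need shifts of 1.0 to 1.5 cm, about 3 to 4.5 times the one on-treatment displacement the protocol cites (10/3.3 = 3.0; 15/3.3 = 4.5). At 3.3 mm the modelled CTV shows no loss.
- The PTV losses are partly built in. When the PTV equals the dose region, any shift costs PTV coverage. Lost PTV margin with a covered CTV is not, in this model, a missed target.
- Section 6.5 builds the CTV and PTV from the GTV, so holding them at baseline size is a convention and not a rule in the plan.
- The model has no proton physics. Range and density changes could lower GTV and ITV dose directly, and would then appear in the recorded data because the proton plan is applied to each scan.
- CTV and PTV are not absent on treatment: 9.4 lists their volumes as weekly endpoints. The overlap endpoint in 9.4 item 5 can also flag some shifts. In the small tumor with 44.3% shrinkage and a 1.5 cm shift, 81.8% of the GTV lies inside the baseline ITV. Recorded organ dose can show over-shoot.

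None of this closes the gap. The overlap endpoint follows the visible tumor and is not a dose. Organ dose does not measure target under-dosing. A CTV or PTV volume is not its coverage. That the result depends on the reference volume is a reason to specify one.

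**Conclusion.** The point holds as an omission that should be corrected. Dose to the CTV and PTV is missing from both the recording list and the analysis list, against the protocol's own description of the PTV and its promise to evaluate dose to the target volumes. Margin under-dosing may go undetected, and comparison with the cited PTV figure is not possible.

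The size is illustrative only. Under the assumed radii, a rigid 1.0 cm shift and baseline-size volumes, GTV and ITV coverage stay at 100% while the CTV is at 93-95% and the PTV at 79-84%. The CTV loss is nil at 0.5 cm or less, and re-derived volumes lose less.

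A reader might infer more: that the recorded target dose will stay near 100%, that the target is in fact being missed, or that the Aim 2 proton error is biased toward finding no problem. The documents support none of these. Section 6.6 records an amount of dose with no percentage metric, no section gives an expected coverage, and proton range effects could move the GTV and ITV dose either with or without margin loss.

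**What to change.** In 6.6 and 9.5 item 4, add the CTV and PTV to the structures on which the initial photon and proton plans are evaluated at each scan. State whether the reference is the baseline volume carried onto the new scan or one re-derived from the current GTV; reporting both would be best, since the two answer different questions. Define the coverage metric in advance and report its change from baseline alongside GTV and ITV dose. Bring the contouring list in 6.6 into line with the weekly CTV and PTV volumes in 9.4. Which of these measures should rank as the main target-dose endpoint is open to debate and need not be settled to close the gap.

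The cost is a wording amendment, some time for contour propagation and editing, and propagation uncertainty that should be acknowledged in the report. The plans are already applied to every scan, so no new scans or patients are needed.

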### **6.7. *Post Therapy/Treatment:***

Subjects will present for an initial post-treatment visit approximately 4-6 weeks after completion of radiation treatment as per the standard of care. Additional follow-up visits will be performed as per the standard of care. Subjects will be considered “off study” on the date of their last radiation treatment.

#### ***6.8. Criteria for Removal from Study***

Any subjects experiencing a serious adverse event (SAE) felt to be related to the study imaging or imaging contrast will be withdrawn from the study. Subjects will be withdrawn from the study if discontinuation of treatment is deemed necessary by the principal investigator to be in their best interest (e.g. an abnormal response of the subject’s malignancy to radiotherapy outside of normal limits is observed, intolerable side effects of radiotherapy occur, clinical deterioration occurs). Subjects may be withdrawn at any time at the discretion of the PI. Any subject withdrawing their consent to participate in the study or their authorization to use their protected health information will be withdrawn from the study. Subjects withdrawn may be replaced at the discretion of the principal investigator.

Subjects may also be withdrawn due to any of the following:

1. Failure to attend outpatient and treatment visits
2. Failure to cooperate and provide tolerability measures

Once the subject has discontinued the study, the primary reason for discontinuing the study must be clearly documented in the subject’s records and on the CRF. The investigator will assess each subject for response at the time of withdrawal.

#### ***6.9 Imaging Acquisition, Archival, and Interpretation***

All images will be acquired at the Hospital of the University of Pennsylvania or the Perelman Center for Advanced Medicine. Image acquisition, archival, and interpretation will be through the Departments of Radiation Oncology and Radiology at the University of Pennsylvania.

### **7.0 DATA COLLECTION AND MANAGEMENT**

All subjects must have a signed Informed Consent Form and a confirmation of eligibility form filled out and signed by a participating investigator prior to receiving a study number.

Case report forms will be used to standardize data keeping and allow entry to a computerized data base.

#### ***Flow of Subject Data***

*Study entry:* Each subject will be evaluated for this study based upon the inclusion and exclusion criteria. If a subject is interested in participating, he/she will be asked to sign and informed consent document after which an eligibility checklist will be completed and

signed. The subject will then be assigned a study number. All study forms: eligibility forms, on study forms, case report forms (CRF), and data entry forms will be coded with the subject's study number to protect subject confidentiality.

*Imaging:* Copies of all imaging for these studies will be maintained by the Department of Radiology at the University of Pennsylvania.

*Follow-up:* Follow up visits will occur as per the standard of care. Subjects will be considered off study as of the date of their last radiation treatment.

## **8.0 Safety and Adverse Events**

The investigator and/or designated research staff will be responsible for detecting, documenting and reporting all events that meet the definition of an Adverse Event (AE) or Serious Adverse Event (SAE) felt to be related to the study imaging or imaging contrast. (see section 6.8)

## **9.0 STATISTICAL CONSIDERATIONS**

### **9.1 *Background:***

Tumor volume, location and proximity to critical normal organs are determined by CT scans prior to the start of radiation treatment. Radiation dosimetry plans are not re-calibrated during the course of a patient's treatment since it is assumed that changes in these variables are negligible. This hypothesis has rarely been studied in a rigorous manner. Dramatic tumor shrinkage or patient weight loss, may cause the radiation energy beam to over-shoot the treatment target and may also increase the radiation dose to nearby critical normal organs.

### **9.2 *Study Design:***

This pilot study will determine changes over time in tumor volume and motion and patient anatomy, as well as dose distributions to normal organs. The study will inform medical decision-making about the need for (and timing of) re-calibration of radiation dosimetry plans. Up to weekly CT and/or serial MR scans (minimum of 3) will be employed to measure changes in tumor volume and motion and patient anatomy in patients receiving definitive radiation therapy (with or without concurrent chemotherapy). This study is not designed to evaluate the CT or MR procedure. CT or MR is simply the imaging method used for precise measurement of tumor volume variables. Enrollment will be stratified by disease site: NSCLC, Head & Neck, GI and Gynecologic tumors. The study will enroll 30 patients in each stratum. This study is descriptive and not powered hypothesis testing.

### **9.3 *Objectives:* To determine changes over time in:**

1. tumor volume variables
2. tumor motion
3. patient anatomy
4. dose distribution to tumor and critical normal organs

**9.4 Endpoints:** To be measured at baseline and then weekly during 7-8 weeks of radiotherapy

1. GTV (gross tumor volume), the volume of the primary tumor visualized on the CT scan
2. ITV (interior tumor volume), the GTV expanded to include interior motion (i.e., breathing or swallowing) such that the tumor resides within the ITV during normal motion
3. CTV (clinical tumor volume), the ITV expanded to include microscopic disease (margins)
4. PTV (planning tumor volume), the CTV expanded by several mm, as determined by radiation dosimetry planning, PTV is considered the ultimate target volume

NOTE the relationship: GTV < ITV < CTV < PTV

5. Dose coverage: at each scan time point, determine the percent of the GTV which resides within the baseline ITV or CTV
5. patient weight and percent weight loss from baseline
6. Radiation dose to critical normal organs based on dose-volume histograms (i.e., 20 Gy to 50% of normal lung tissue)

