## Quantification of Tumor and Organ at Risk (OAR) Volume and Motion Path Changes during Definitive Photon or Proton Beam Radiotherapy

respiratory motion when calculating appropriate target volume margins. The distal esophagus can move 0.8cm radially and 1.8cm axially (Yaremko) and the pancreas can move 2.4 +/- 1.6 cm axially (Bussels). Lung tumors are significantly affected by respiratory motion and move 5-10 mm during quiet breathing and as much as 4.5 cm (Stevens) with deeper breaths. Therefore, accounting for respiratory motion can be extremely important for targeted radiation therapy.

The course of radiation treatment often lasts longer than 8 weeks. For patients with head and neck and gastrointestinal cancers, maintaining adequate nutrition during this time can be challenging. Studies have shown that about 35% of patients with head and neck cancers experience >10% weight loss and patients with gastrointestinal cancers experience weight loss ranging from 0-12% (Milano, Talamonti, Lin). Significant weight loss results in changes in patient anatomy, which can distort radiation dose distribution and therefore treatment efficacy.

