### 3.0 SPECIFIC AIMS/OBJECTIVES

**Specific Aim 1:** To estimate the degree of tumor volume, tumor motion and patient anatomy change during treatment with photon beam radiotherapy.

- 1a. To estimate the degree and impact of tumor volume change during the course of definitive photon radiotherapy treatment in lung cancers, head and neck cancers, gastrointestinal cancers (including but not limited to colorectal and rectal cancers) and gynecological cancers.
- 1b. To estimate the degree and impact of tumor motion (anatomic location) change during the course of definitive photon radiotherapy treatment in lung cancers, head and neck cancers, gastrointestinal cancers (including but not limited to colorectal and rectal cancers and gynecological cancers).
- 1c. To estimate the degree and impact of changes in patient anatomy during the course of definitive photon radiotherapy treatment in head and neck and upper gastrointestinal cancers.

Hypothesis: Tumor volume and motion will change over the course of radiation treatment in patients with lung cancers, head and neck cancers, gastrointestinal cancers (including but not limited to colorectal and rectal cancers) and gynecological cancers. The weight loss experienced by patients with upper gastrointestinal and head and neck cancers will have a significant impact on their anatomy. These changes will alter the dose distribution of the photon beam treatment plans, possibly limiting radiation dose delivery to the target volumes and increasing radiation toxicity to surrounding critical structures.

**Specific Aim 2:** To estimate the error if tumor volume, tumor motion and patient anatomy change during treatment with proton beam radiotherapy.

- 2a. To generate simulated proton beam plans using serial CT or MR imaging obtained from either photon or proton beam patients to estimate the dosimetric error if these changes are unaccounted for during proton treatment.

[figure not shown]
Hypothesis: The changes in tumor volume and motion and patient anatomy will have a greater effect on appropriate dose distribution in plans using proton beam therapy compared to photon beam therapy given the need for more accurate target delineation in proton beam therapy.

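### The tumor-motion measure is a containment percentage, mislabelled as dose coverage and capped at 100%, so it does not estimate the degree of location change; its companion Wilcoxon test compares unlike structures

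*Combined protocol and SAP*

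**What the plan says.** Aim 1b in Section 3.0 is "To estimate the degree and impact of tumor motion (anatomic location) change during the course of definitive photon radiotherapy treatment", and Section 4.0 says the scans will be "analyzed for changes in tumor volume and tumor anatomic location".

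The measure that serves this aim is in Section 9.4 item 5: "Dose coverage: at each scan time point, determine the percent of the GTV which resides within the baseline ITV or CTV". Section 6.6 describes the same quantity with one reference volume only: "Each GTV will be compared to the initial ITV volume to determine what percent of the GTV resides within the initial ITV". It then adds: "This value will be used to evaluate changes in tumor motion". Section 9.5 item 2, the tumor-motion analysis, summarizes this percentage at each scan and plots its mean. It also calls for a paired Wilcoxon signed-rank test of baseline ITV or CTV against the GTV at later scans. A note in Section 9.4 orders the volumes as GTV < ITV < CTV < PTV.

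Dose is handled elsewhere. Section 6.6 says "The amount of radiation dose to each GTV, ITV and critical normal structures will be recorded", and Section 9.5 item 4 analyzes it. Section 6.6 also compares later ITVs with the initial one without naming a metric. ITV volume is an endpoint (9.4 item 2) whose change from baseline falls under 9.5 item 1.

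**The concern.** Three things look wrong.

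- **Label.** The quantity called dose coverage is purely geometric. A reader of the results would take it for a dosimetric finding.
- **Ceiling.** A percentage that starts at 100% and can only stay there or fall does not register a shift until the tumor leaves the reference volume. Aim 1b asks for degree as well as impact, and no endpoint in 9.4 gives a displacement. A mean that stays near 100% could be reported as no change in motion while displacement grows.
- **Test.** Baseline ITV or CTV and later GTV are different structures that the plan itself ranks by size. A difference between them exists before anything has changed, so a small p value is not evidence of motion.

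The reference volume is also open. It is ITV or CTV in 9.4 but ITV alone in 6.6, and the CTV is built from the GTV in 6.5 but from the ITV in 9.4 item 3.

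**Working it through.** The plan gives no figure for the motion endpoint or its test. Its only related number is the sample size, 4 strata × 30 = 120, which has no power derivation.

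**Inputs from the documents (Section 2.0).** For NSCLC, "a median GTV reduction of 44.3% at 50Gy". For head and neck cancer, 69.5% GTV reduction and 3.3 mm median displacement. Lung tumors "move 5-10 mm during quiet breathing".

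**Assumptions.** Spherical GTV with concentric shrinkage; baseline radius R₀ of 20 or 10 mm; margin m of 2.5 or 5 mm (half of the cited 5-10 mm) or 10 mm (a wider CTV). The documents state no ITV or CTV margin.

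**1. Ceiling.** With shrinkage s, the current radius is r = R₀(1 − s)^(1/3); the factor is 0.823 at 44.3% and 0.673 at 69.5%. Containment is 100% for every shift d ≤ R₀ + m − r. For example, with R₀ = 20, m = 5 and s = 69.5%: 25 − 13.46 = 11.5 mm.

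| Largest shift still reading 100% (R₀ = 20 mm) | s = 0 | s = 44.3% | s = 69.5% |
|---|---|---|---|
| m = 2.5 mm | 2.5 mm | 6.0 mm | 9.0 mm |
| m = 5 mm | 5.0 mm | 8.5 mm | 11.5 mm |
| m = 10 mm | 10.0 mm | 13.5 mm | 16.5 mm |

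The cited 3.3 mm shift reads 100% at any margin of 3.3 mm or more.

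**2. Above the ceiling.** Let R = R₀ + m. The reading is the overlap volume π(R + r − d)²[d² + 2d(R + r) − 3(R − r)²]/(12d), divided by (4/3)πr³. With R = 25, r = 20, d = 10: (1225 × 925/120)/10,667 = 88.5%. The same 10 mm shift reads 98.5% at 44.3% shrinkage and 100% at 69.5%. With no shrinkage but m = 10 instead of 5, it reads 100% instead of 88.5%. One shift therefore gives different readings according to shrinkage and choice of reference.

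Shrinkage usually raises the reading, but no simple rule holds for very large shifts. At R₀ = 20, m = 2.5, d = 23 mm it goes 31.8, 34.3, 36.3%. At R₀ = 10, m = 2.5, d = 15 mm it goes 20.7, 19.4, 17.2%.

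**3. Motion doubling while the tumor shrinks.** Displacement components are taken as independent normals (40,000 draws). The median shift goes from 3.3 mm with no shrinkage to 6.6 mm with 69.5% shrinkage.

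| R₀, m (mm) | Mean containment before | After |
|---|---|---|
| 20, 5 | 99.9% | 99.8% |
| 20, 2.5 | 97.8% | 99.0% |
| 10, 5 | 99.7% | 96.3% |
| 10, 2.5 | 95.3% | 87.6% |

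For the larger tumor the mean is flat or rises while motion doubles. Small tumors do respond.

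**4. Wilcoxon test.** If all n differences have one sign, the exact two-sided p is 2 × 2⁻ⁿ. For n = 30 this is 1.9e-9, and p is already 0.031 at n = 6. With unchanged GTVs and a larger reference, all signs agree; shrinkage widens the gap. The difference reaches zero only when the GTV grows by (R/R₀)³ − 1: 42% (R₀ = 20, m = 2.5), 95% (20, 5) or 238% (10, 5).

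Simulations of 30 patients with an assumed log-scale SD of 0.2 for volume change, judged at two-sided 0.05, show the limits:

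- No mean change: rejection was 83% at a 1 mm margin and 100% at 2-5 mm.
- Mean growth that roughly offsets the margin: rejection was 34% (1 mm, +20%) and 16% (3 mm, +50%).

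**The case against.** The strongest defense is that containment is the clinically relevant quantity: a shift that stays inside the margin has no geometric consequence, so 100% is the right reading. That stands for impact, and the measure should be kept. It also limits what can be said about Section 9.5 item 6. A reader might infer that item 6 cannot be answered because nothing measures location. In fact it concerns volume or location changes that lead to over-shoot or higher organ dose, which containment and the recorded doses partly address.

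Other stronger readings also go too far.

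- **That the study lacks dose data.** Dose to GTV, ITV and organs is recorded and analyzed; only the label is wrong.
- **That the Wilcoxon test is significant whatever happens.** It can fail to reject if GTVs grow enough, or where the ITV equals the GTV, which is possible because 6.5 creates an ITV only in 4D planning CTs. The 1.9e-9 also needs all 30 patients scanned at that time point, while CT is only up to weekly and MR a minimum of three.
- **That motion has no like-with-like analysis at all.** Change in ITV volume is tested under 9.5 item 1 and carries some information on the motion envelope. It mixes motion with shrinkage, however, and gives no displacement.
- **That ITV-based and CTV-based percentages will be pooled.** Section 9.5 does not say so; it simply gives no rule.

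Finally, the study is a descriptive pilot, the test gates no decision, and the sizes above rest on assumed geometry. All true. But a descriptive study depends on its descriptive measures, and the ceiling exists for any positive margin.

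**Conclusion.** The point holds for the degree part of Aim 1b. The motion measure is mislabelled and does not register a shift until part of the GTV leaves the reference volume. Beyond that, it mixes shift with shrinkage and margin. With a 20 mm radius and 5 mm margin, shifts of 5.0 to 11.5 mm can go unseen, depending on shrinkage, and a doubled median shift moves the mean by 0.1 point. For a 10 mm radius and 2.5 mm margin the measure does respond, from about 95% to 88%. So it is an insensitive and confounded measure of location, not an empty one.

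The companion test says nothing about motion wherever the reference is larger than the GTV and the GTV is stable or shrinking, which is the situation that Sections 2.0 and 9.4 describe.

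The ceiling and the ordering of volumes follow from the plan's definitions. The millimeter and percentage figures rest on spheres, concentric shrinkage and assumed radii, margins and displacement distribution. The harm is an uninformative motion estimate and a misleading p value, not lost power. It should be fixed.

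**What to change.** 1. Rename 9.4 item 5 geometric containment and keep it as the geometric-miss measure. Report it separately against the baseline ITV and the baseline CTV. The passages on the reference volume (6.6 and 9.4) and on how the CTV is built (6.5 and 9.4) must be reconciled.
2. Delete the Wilcoxon test of baseline ITV or CTV against later GTV from 9.5 item 2. Keep the like-with-like comparisons in 9.5 item 1.
3. Add GTV centroid displacement from baseline in mm, per axis and in 3D, using the same scan alignment that containment needs. State that alignment, and state which GTV is meant, since 9.4 item 1 describes the primary tumor and 6.5 includes enlarged nodes. Report the median and 95% CI at each scan, beside containment and volume.

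**Cost.** Changes to endpoint and analysis wording, plus analysis time. No new scans are needed: 6.6 already requires contours on each scan, and containment cannot be computed without alignment to baseline. The documents state no registration method, so that effort cannot be sized from them.

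**Downside.** Displacement carries registration error, including MR to CT, and a centroid moves when a tumor shrinks asymmetrically. It should therefore never be shown alone.
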